7.3.1.3. Measure of prevalence (*P. falciparum* infection)

The prevalence of *P. falciparum* infection will be evaluated on the cross-sectional ADI samples only. At each pre-defined timepoint (see protocol section 6.5) the prevalence (number of subjects with *P.falciparium* infection/total number of subjects) of *P. falciparum* infection will be calculated by group together with 95% CIs. Graphical presentations of the prevalence over time will be produced. Results per site and overall will be summarized in tables. In addition the number of positive prevalent infections will be analyzed by a negative binomial regression to compare the groups (Fx012-14, Fx017-20, R012) against the control to obtain vaccine efficacy estimates and corresponding 95% CI (applying the same strategy as for all episodes in section 7.3.1.2).

The prevalence of gametocytemia will be tabulated for each group (Fx017-20, Fx012-14, R012-20, R012-14 and control) at each monthly cross-sectional visit (from M0 until M20) and thereafter at each three-monthly cross-sectional visit (from M23 until M50).

Within gametocytes positive slides the mean male/female ratio will be tabulated by group and time point and by site. Within parasitemia positive subjects the geometric mean will be tabulated by group and time point and by site.

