7.3.1.1. Strategy of analysis and rationale

The strategy of analysis for the present study has been developed considering the following points:

- Prevalent infections are only captured by ADI during the cross-sectional surveys performed at pre-defined timepoints throughout the study. Incident infections are captured via both ADI at cross-sectional surveys and via passive detection upon spontaneous presentation at health centers (see Section 4.2 of the protocol for case definitions of *P. falciparum* infections). Episodes of clinical malaria will be treated when diagnosed. Samples collected at cross-sectional visits in asymptomatic children will not be processed in real time and will not lead to systematic treatment.
- Vaccine efficacy against prevalent *P. falciparum* infections at the successive cross-sectional surveys is an important measure as it is not influenced by care seeking behavior and possibly less influenced by blood-stage immunity. Reducing the prevalence of blood-stage infections at successive timepoints will be a good indicator of the potential to reduce transmission as it is directly associated with the potential to infect mosquitoes.
- Vaccine efficacy against first or only episode of incident *P. falciparum* infection or against first or only episode of clinical malaria minimizes the bias related to differential acquisition of blood-stage immunity in the vaccine and Control groups, and is assumed to be the best way to assess the biological effect of the third dose fractioning and spacing.
- Vaccine efficacy against all episodes of clinical malaria is more relevant to public health but over longer time periods. There is a possibility of bias related to the fact that it will compare a Control group with frequent exposure and an intervention group with reduced exposure and a different build-up of blood-stage immunity over time, possibly influencing health seeking behaviors (hence the importance of also evaluating vaccine efficacy against prevalent infection and first or only episode).
- Considering the measures of incidence:
 - For group comparisons with identical calendar time follow-up periods, the incidence rates will be directly compared. The incremental vaccine efficacy estimate is defined as 1-Incidence Rate Ratio in each group.

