7.3.1.2. Measures of incidence (*P. falciparum* infection and clinical malaria)

First or only episode

Vaccine efficacy against first or only episode of incident *P. falciparum* infection or clinical malaria will be analyzed by Cox regression stratified by study site, and overall. The 95% CI and p-values of the vaccine efficacy estimates (1- Hazard Ratio) will be calculated from this model. Cumulative incidence graphs will be produced.

• All episodes

Vaccine efficacy against all episodes of clinical malaria will be analyzed by negative binomial regression allowing for interdependence between episodes within the same subject (non-linear mixed model with over dispersion parameter estimated from the random effect). The 95% CI and p-values of the vaccine efficacy estimates (1- Incidence Rate Ratio) will be calculated from this model. In case models do not converge or showed poor fit, alternative negative binomial models without random effects will be applied. fourteen days following an episode meeting the case definition under evaluation will be subtracted from the follow-up time. The distribution of the total number of events per subject will be tabulated by group. Results per site and overall (adjusted for site as a fixed effect) will be summarized in tables and forest plots.

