7.3.2. Additional considerations

7.3.2.1. All planned VE Analyses and corresponding risk periods

This section describes all VE analyses (planned in protocol and additional analyses).

For each endpoint, the time at risk will be calculated separately. The time at risk will be counted in days, and expressed as person years at risk (days/365.25). In order to avoid mathematical problems because of time equals zero when an event occurred the same day that the time at risk started, the first day counts as 1 thus the duration is calculated as (date of event or censoring – date of start follow up +1). Time at risk will end at the date of next visit minus 1 to avoid including post safety and efficacy data that may have occurred on the same day.

For endpoints evaluating all episodes where time at risk does not end when the episode meets the case definition, 14 days following the episode will be subtracted from the time at risk (day of episode + 14). If an episode is detected during a period of time not counting for the time at risk it will not be included in the analysis however a table will be presented showing the number of such episodes not included in the analysis.

Table 3 Risk periods for clinical malaria & incident infection for the exposed set

Risk Period (months)	Start of risk period (at subject level)	End of risk period (at subject level)*	Group comparisons	Clinical malaria	Incident Infection
M20 analys	es				
[0-14]	Day of first vaccination of RTS,S or	Date of Month 14 visit – 1 or drop out date	Fx017-20 vs control Fx012-14 vs control	First or only- and all episodes First or only-	First or only episode First or only
	control vaccine	from study conclusion, whichever occurs first	R012-20 +R012-14 vs control Fx012-14 Vs R012-20	and all episodes First or only- and all episodes First or only-	episode First or only episode First or only
[0-20]	Day of first vaccination of	Date of Month 20 visit – 1 or	+R012-14 Fx017-20 vs control	and all episodes All episodes	episode First or only episode
	RTS,S or control	drop out date from study	Fx012-14 vs control	All episodes	First or only episode
	vaccine	conclusion, whichever	R012-20 vs control	All episodes	First or only episode
		occurs first	R012-14 vs control	All episodes	First or only episode
			Fx012-14 Vs R012-20	All episodes	First or only episode
			Fx012-14 Vs R012-14	All episodes	First or only episode
M32 analys		Data af Marath	F-047 00	All:	LAIA

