[0-26]	Day of first vaccination of	Date of Month 26/32 visit – 1 or	Fx017-20 vs control Fx012-14 vs control	All episodes	NA
[0-32]	RTS,S or	drop out date		All episodes	
	control	from study	R012-20 vs control	All episodes	
	vaccine	conclusion,	R012-14 vs control	All episodes	
	Vaccino	whichever occurs first	Fx012-14 Vs R012-20 Fx012-14 Vs R012-14	All episodes All episodes	
M50 analys					
[0-38]	Day of first	Date of Month	Fx017-20 vs control	All episodes	NA
	vaccination of	38 visit – 1 or	Fx012-14 vs control	All episodes	
	RTS,S or	drop out date	R012-20 vs control	All episodes	
	control	from study	R012-14 vs control	All episodes	
	vaccine	conclusion,	Fx012-14 Vs R012-20	All episodes	
10.50		whichever occurs first	Fx012-14 Vs R012-14	All episodes	
[0-50]	Day of first	Date of Month	Fx017-20 vs control	All episodes	NA
	vaccination of	50 visit – 1 or	Fx012-14 vs control	All episodes	
	RTS,S or	drop out date	R012-20 vs control	All episodes	
	control vaccine	from study conclusion,	R012-14 vs control	All episodes	
	vaccine	whichever	Fx012-14 Vs R012-20	All episodes	
		occurs first	Fx012-14 Vs R012-14	All episodes	
		Coodio illot	Fx017-20 vs R012-14	All episodes	
			Fx017-20 vs Fx012-14	All episodes	

^{*} if visit date and last contact date are both missing then subjects will be censored at month [x] times 30.5 days post dose 1.

Clinical malaria

For endpoints evaluating the first or only clinical malaria, subjects who withdraw from the study before the study end will contribute to the time at risk computation. This will be explained with the help of the following figure. In these illustrative examples, for the sake of simplicity, it has been considered that visits were effectively conducted at exact monthly intervals.

	M1 30.5d	M2 30.5d	M3 30.5d	M4 30.5d	M5 30.5d	M6 30.5 d	M7 30.5 d	M8 30.5 d	M9 30.5 d	M10 30.5d	-negative +positive
Subject	-	-	-			-	-	+			. missing
Α							—				
Subject	-	-	-	+	-	+	-	-	-	-	
В			—		—				→		

Example: Subject A has two missed visits at month 4 and month 5, and an episode of clinical malaria at start of month 8. This subject will be considered to have an event at month 8, and therefore the time at risk will be (30.5d*7months) 214 days.

For endpoints evaluating all episodes 14 days following each episode will be subtracted from the time at risk (day of episode + 14). For subject B the time at risk will be (30.5*10 months) - (2*14 days) 277 days.

Incident infection

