Only subjects with a confirmed negative blood slide at the beginning of the follow-up period (defined in Table 3) will be included in the analysis. The subjects will be followed-up until either having a case, or being censored (having a missing cross-sectional visit or being a drop-out whichever occurs first).

Example: the subject A described in the previous example would have been censored at the start of month 4 and contributes (3*30.5) 92 days to the time at risk.

Risk periods for prevalent parasitemia & Gametocytemia

At month 20 there are two types of analysis that will be presented:

- First, the prevalence of parasitemia/gametocytemia will be tabulated for each group (Fx017-20, Fx012-14, R012-20, R012-14 and control) at each cross sectional visit (from M0 until M20).
 - Within gametocytes positive slides the mean male/female ratio will be tabulated by group and time point and by site.
 - Within parasitemia positives the geometric mean with will be tabulated by group and time point and by site.
- Second, an analysis with endpoint all episodes of prevalent infections within risk period [M1-M20] will be performed comparing the groups (Fx017-20, Fx012-14, R012-20, R012-14) with the control. In this analysis subjects with missing visits before the last contact date will only contribute to the time at risk at the time periods

they are not missing. See example below. The subject contributes (3*30.5) + (2*30.5) = 153 days to the time at risk.

• In both analyses described above subjects with clinical malaria (case definition 1 or 2) at start day of detection of parasitemia + subsequent 14 days will be excluded.

At month 32 and month 50 the following analyses will be performed for each group, at each cross sectional visit and by site:

- the prevalence of parasitemia/gametocytemia
- male/female ratio for gametocytes positive slides
- and geometric means for parasitemia positives

Table 4 Risk periods for clinical Malaria & incident infection for the per protocol set: Comparisons with equal calendar times

Risk Period (months)	Start of risk period (at subject level)	End of risk period (at subject level)*	Group comparisons	Clinical Malaria	Incident infection
Analyses 1	2 months post do	se 3:			
• Prima	ary objective: incr	emental efficacy of f	ractional dose versus fu	II dose	
• Seco	ndary objective: v	accine efficacy of al	l groups versus controls	;	

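### The SAP's rules conflict on whether each positive survey slide removes 14 days of time at risk in the M1-M20 prevalent-infection model; if it does, efficacy of a protective schedule is biased upward

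*SAP*

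**What the plan says.** Two sets of rules bear on the survey-infection model for Month 1 to Month 20.

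The general rules:
- SAP 7.3.1.3 compares vaccine groups with Control on the number of positive survey infections, using negative binomial regression and "applying the same strategy as for all episodes in section 7.3.1.2".
- SAP 7.3.1.2, the section referred to, states that "fourteen days following an episode meeting the case definition under evaluation will be subtracted from the follow-up time".
- SAP 7.3.2.1 repeats this for all-episodes endpoints in general: "14 days following the episode will be subtracted from the time at risk (day of episode + 14".
- The part of 7.3.2.1 on prevalent parasitemia places the survey model in that class: "an analysis with endpoint all episodes of prevalent infections within risk period [M1-M20] will be performed".

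The rules written for the survey endpoint, also in that part of 7.3.2.1:
- A child contributes time only for periods whose visits are not missing. The example reads "The subject contributes (3*30.5) + (2*30.5) = 153 days to the time at risk".
- The only 14-day provision stated there is that "subjects with clinical malaria (case definition 1 or 2) at start day of detection of parasitemia + subsequent 14 days will be excluded".

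On treatment, SAP 7.3.1.1 says that survey samples from asymptomatic children "will not be processed in real time and will not lead to systematic treatment". Protocol 6.4.2 agrees. The rationale for Protocol Amendment 3 explains the 14 days by drug clearance and by comparability with the earlier Phase III efficacy data.

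**The concern.** Removing time after a clinical episode makes sense: the child is treated, and for a while is not at risk of a new countable episode. An asymptomatic survey positive is not treated, so the clearance argument does not carry over. Monthly surveys are also at least 21 days apart, so the 14 days removed never contain the next scheduled survey. Nothing is unobserved; only the denominator falls.

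The denominator then depends on the outcome. The arm with more positive slides loses more time, its rate rises more, and the rate ratio moves away from one. SAP section 10 presents this model as the summary efficacy measure for prevalent infection up to Month 20. The SAP's prevalence section gives no other between-group estimate, whereas Protocol 11.7.3 had planned relative risks at each survey. A programmer following 7.3.1.2, 7.3.1.3 and the general rule would subtract 14 days per positive slide; one following the endpoint-specific text would not.

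**Working it through.** **The plan's own figures.** Survey endpoint: 3 × 30.5 + 2 × 30.5 = 152.5, printed as 153 days, with no 14-day term. Clinical malaria, all episodes: "For subject B the time at risk will be (30.5*10 months) - (2*14 days) 277 days", and 305 − 28 = 277. Both reproduce. The subtraction is shown for clinical malaria and is absent for the survey endpoint.

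**Inputs.** 14 days per episode (SAP 7.3.1.2, 7.3.2.1). Survey interval L = 30.5 days, as in the SAP examples; the allowed range is 21-35 days (visit-interval table, SAP section 2). Slide prevalence per survey is not given, so it is assumed, from 5% to 50%.

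**Formulas.** With slide prevalence p, each survey yields on average p positives and L − 14p days.
- Rate inflation = L / (L − 14p).
- Efficacy without subtraction = 1 − p₁/p₀.
- Efficacy with subtraction = 1 − (p₁/p₀) × (L − 14p₀)/(L − 14p₁).

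Here p₀ is Control and p₁ is the vaccine group.

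**One line in full.** For p₀ = 20% and p₁ = 14%, efficacy without subtraction is 30.0%. Control has 30.5 − 2.8 = 27.7 days per survey and the vaccine group 30.5 − 1.96 = 28.54. Control's rate is inflated by 30.5/27.7 = 1.101. Efficacy becomes 1 − 0.70 × 27.7/28.54 = 32.1%.

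| Assumed Control prevalence | Control rate inflation | Efficacy reported, true 10% | true 30% | true 50% |
|---|---|---|---|---|
| 5% | 2.3% | 10.2% | 30.5% | 50.6% |
| 10% | 4.8% | 10.4% | 31.0% | 51.2% |
| 20% | 10.1% | 10.9% | 32.1% | 52.4% |
| 30% | 16.0% | 11.4% | 33.2% | 53.7% |
| 50% | 29.8% | 12.6% | 35.7% | 56.5% |

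With true efficacy of zero, p₁ = p₀, the inflation cancels and the bias is nil.

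**Sensitivity to spacing.** At 20% prevalence the rate inflation is 15.4% for 21-day spacing and 8.7% for 35-day spacing; at 50% it is 50.0% and 25.0%.

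**Simulation.** Negative binomial fits with 300 children per group, 20 surveys and risk varying strongly between children (40 runs per setting) gave larger Control rate inflation: about 12-23% at 5% prevalence, 19-31% at 20% and 38-48% at 50%. For true efficacy of 30% or 50%, the efficacy shift stayed close to the table: about 1 to 3 points up to 20% prevalence, 3 to 4 at 30% and 5 to 6 at 50%.

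**Extreme case.** This shows why the denominator is wrong in kind. A child positive at 20 monthly surveys, counted at 30.5 days each, would have 610 − 280 = 330 days. The rate is 20/330 × 365.25 = 22.1 per year, against 20/610 × 365.25 = 12.0 without subtraction, which is the most that monthly surveys allow.

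**The case against.** The strongest reply is that the endpoint-specific text governs. It has its own time-at-risk rule, its 14 days attach to clinical malaria, which is the treated event, and its example has no subtraction. If every positive slide already cost 14 days, a separate clinical-malaria rule would be partly redundant. The cross-reference in 7.3.1.3 may concern only the choice of model, since the paragraph it points to opens with clinical malaria. On that reading the plan is already sound: an offset of log(30.5 × n) differs from log(n) by a constant, which leaves efficacy unchanged.

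Much of this stands. It makes the intent uncertain, so a reader who infers that the SAP definitely subtracts 14 days for every survey positive goes beyond the documents. But it does not settle the matter. No sentence exempts the survey endpoint from a rule stated for all-episodes endpoints, and the SAP gives it that label. The figure showing the example child's slide results is not visible, so the example cannot show that a positive slide went without a deduction.

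It is also fair that the stakes are limited. SAP section 8 makes secondary endpoints outside the testing hierarchy descriptive, and prevalence by group at each survey, which uses no person-time, is still tabulated.

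**Conclusion.** The rules conflict and must be reconciled. Followed as stated, the general rule biases the efficacy of a protective schedule upward; followed as stated, the endpoint-specific text does not.

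Under the general rule, with 30.5-day spacing and true efficacy of 10-50%, the overstatement is 0.2-0.6 percentage points at 5% Control prevalence, 0.4-1.2 at 10%, 0.9-2.4 at 20%, 1.4-3.7 at 30% and 2.6-6.5 at 50%. These prevalences are assumptions.

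A reader might infer that efficacy is overstated by 10-30%. The documents do not support that. In the simple calculation, 10-30% is the inflation of rates, it needs a slide prevalence of about 20-50%, and most of it cancels between arms. Nor are all survey positives documented as untreated: the statements cover asymptomatic children, while clinical malaria is treated. The primary endpoint, first or only clinical malaria, is unaffected.

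**What to change.** State in SAP 7.3.1.3 and 7.3.2.1 that the 14-day subtraction does not apply after an asymptomatic positive survey slide. Use the log of the number of evaluable survey slides read in M1-M20 as the offset for the count of positive slides. Slides excluded under the rule for clinical malaria plus 14 days should leave both the count and the offset, so that numerator and denominator match. Missed surveys then drop out without being turned into 30.5-day blocks, and the estimate returns to the relative-risk scale of Protocol 11.7.3.

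The cost is one sentence and one offset. Compared with the general rule, the reported efficacy of a protective schedule will be slightly less favourable.

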6.7.3. Laboratory assays

Please refer to [APPENDIX A](#) for a detailed description of the assays performed in the study. Please refer to [APPENDIX B](#) for the address of the clinical laboratories used for sample analysis.

Serological assays for the determination of anti-CS antibodies will be performed by ELISA at a laboratory designated by GSK Biologicals using standardized and validated procedures (refer to [Table 16](#)).

Serological assays for the determination of anti-CS antibody avidity will be performed by ELISA at a laboratory designated by GSK Biologicals using standardized procedures (refer to [Table 16](#)).

Serological assays for the determination of anti-HBs antibodies will be performed by chemiluminescence enzyme immunoassay (CLIA) at a GSK Biologicals laboratory using standardized and validated procedures (refer to [Table 16](#)).

Table 16 Humoral immunity (antibody determination)

System*	Component	Method	Kit / Manufacturer	Unit	Cut-off	Laboratory
SERUM	Plasmodium falciparum.Circumsporozoite Protein.R32LR Ab.IgG	ELISA	in house	EU/ml	0.5	CEVAC
SERUM	Hepatitis B Virus.Surface Ab	CLIA	ADVIA Centaur anti-HBs2 (Siemens Healthcare)	mIU/ml	6.2	GSK Biologicals**
SERUM	Plasmodium falciparum.Circumsporozoide Protein.R32LR Ab.IgG Avidity	ELISA	in house	%	Not applicable	CEVAC

CCI

** GSK Biologicals laboratory refers to the Clinical Laboratory Sciences (CLS) in Rixensart, Belgium; Wavre, Belgium.

Ab: antibody

CEVAC: Center for Vaccinology, Ghent, Belgium

CLIA: chemiluminescence enzyme immunoassay

ELISA: Enzyme-linked immunosorbent assay

EU/ml: ELISA unit per milliliter

IgG: Immunoglobulin G

mIU/ml: milli-international unit per milliliter

Table 17 Assessment of *P. falciparum* infection

System	Component	Method	Unit	Laboratory
Whole Blood*	Plasmodium falciparum parasites**	Not applicable***	Not applicable	KEMRI/USAMRU-K, WRP, Malaria Diagnostics Center, Kisumu§

KEMRI/USAMRU-K, WRP: Kenya Medical Research Institute / US Army Medical Research Unit Kenya, Walter Reed Project.

* The incidence of *P. falciparum* infection assessed by PCR and parasite genotyping will be evaluated in an ancillary study, using samples collected as described in the present protocol (see Table 20).** *P. falciparum* parasite count includes blood-stage parasites and gametocytes counts.

*** Method used will be blood slide microscope reading.

§ And/or other GSK designated laboratory.

Table 18 Hematology and biochemistry

System	Component	Method	Scale	Laboratory

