2. STUDY DESIGN

Figure 1 Study design: clinic visits

04-SEP-2019 10

In addition to the clinic visits presented in the figure above, parasite prevalence will be assessed at the following visits (these will be fieldworker visits or clinic visits depending on the timepoint and the group):

Figure 2 Study design: visits for assessment of parasite prevalence

Visits for para	site prevalence												
Year 1	Visit 2	Visit 3	Visit 4	Visit 6	Visit 7	Visit 8	Visit 9	Visit 10	Visit 12	Visit 13	Visit 14	Visit 15	Visit 16
	Day 0	Month 1	Month 2	Month 3	Month 4	Month 5	Month 6	Month 7	Month 8	Month 9	Month 10	Month 11	Month 12
Year 2		Visit 17	Visit 18	Visit 19	Visit 20	Visit 21	Visit 22	Visit 23	Visit 24			Visit 26	
		Month 13	Month 14	Month 15	Month 16	Month 17	Month 18	Month 19	Month 20			Month 23	
Year 3			Visit 27			Visit 29			Visit 30			Visit 32	
			Month 26			Month 29			Month 32			Month 35	
Year 4			Visit 33			Visit 35			Visit 36			Visit 37	
			Month 38			Month 41			Month 44			Month 47	
Year 5			Visit 38										
			Month 50										

04-SEP-2019 11

- Experimental design: Phase IIB, randomized, open-label, controlled, multi-centric, study with five parallel groups.
- Randomization: minimization method accounting for center was used.
- **Study groups:** 5 study groups are defined for the study, each consisting of 300 subjects (aged 5-17 months).
- Treatment allocation: randomized.
- Blinding: open.
- Efficacy surveillance:
 - Capture of malaria cases: malaria cases will be captured by passive case detection (PCD). Parents/LARs will be advised to present their child to the health center if the child is unwell. Care will be administered according to local recommendations. All children with fever and/or history of fever will have a blood sample taken for the evaluation of vaccine efficacy (blood slide and filter paper for polymerase chain reaction [PCR]). All anti-malaria treatments administered during the study should be recorded in the subject's eCRF.
 - Cross-sectional surveys: to evaluate the vaccine efficacy against incident and prevalent *P. falciparum* infections, monthly cross-sectional surveys will be performed from Day 0 until Month 20 to measure *P. falciparum* parasitemia. Thereafter until study end (Month 50) parasitemia will be measured every three months. Blood slides from cross-sectional surveys will not be read in real time.

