8. ANALYSIS INTERPRETATION

Vaccine efficacy estimates with a lower limit of the 95% CI above 0 are to be considered statistically significant.

If the standard schedule of 3 full doses at month 0, 1 and 2 is not statistically significantly superior to the control group in terms of efficacy, the other secondary objectives should be interpreted in the light of this finding.

In order to control alpha not only for the primary objective but also for the secondary objective of incremental efficacy over the 12-month period post-dose 3 of a schedule with a fractional dose at month 7 versus 3 full doses, a sequential approach will be implemented (hierarchical testing). The endpoints will be analyzed sequentially and any conclusion on the secondary endpoint will be conditional to reaching the primary endpoint. All other secondary endpoints should be interpreted descriptively.

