11.1.1.2. Laboratory data

Missing laboratory results (including immunological data) will not be replaced.

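### The planned mean male/female gametocyte ratio is undefined on slides with no female and, when few gametocytes are counted, depends on the count, so arms with the same sex ratio could show different values

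*SAP*

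**What the plan says.** SAP 7.3.1.3 plans the summary as follows: "Within gametocytes positive slides the mean male/female ratio will be tabulated by group and time point and by site". SAP 7.3.2.1 repeats the sentence for the Month 20 analysis. For Months 32 and 50 it lists "male/female ratio for gametocytes positive slides", by group, cross-sectional visit and site, without the word mean.

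Neither section gives a formula, a rule for slides with no female, a minimum count or a weighting. The general rule in SAP 11.1.1.2 is: "Missing laboratory results (including immunological data) will not be replaced".

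Protocol 6.7.3 says that the slide reading's "parasite count includes blood-stage parasites and gametocytes counts"; it does not mention sexing the gametocytes. The ratio sits under SAP 7.3.1, which covers efficacy analyses planned in the protocol, but protocol 11.7.3 does not contain it and SAP section 10 does not list it as an addition. It is not among the objectives or endpoints of either document, and no test or confidence interval is planned for it.

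**The concern.** A mean taken within positive slides reads naturally as an average of per-slide ratios, and that average has two weaknesses.

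First, a slide on which only males are seen has a zero denominator. If a ratio that cannot be computed is treated as missing and not replaced, the slides that drop out are exactly the male-only ones.

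Second, the mean of the ratios that remain is not the population ratio unless counts are large. With one gametocyte on the slide, the only ratio that can be defined is 0. With a handful, the division by a small and variable number of females pushes the average above the truth. The printed value therefore reflects gametocyte count as well as sex ratio.

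The table compares groups, and the vaccine schedules may change parasite burden. A difference in the printed ratio could then be read as a biological effect on sex ratio when only the count differs.

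**Working it through.** The documents state no figure for the sex ratio, so there is nothing of the plan's own to reproduce. The check asks how the planned summary behaves when the true sex ratio is held fixed and only the count varies.

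Inputs from the SAP: the ratio is averaged over gametocyte-positive slides (7.3.1.3), and missing laboratory results are not replaced (11.1.1.2). Assumptions not in the documents: gametocytes counted per slide follow a Poisson distribution with mean λ, restricted to slides with at least one, and each gametocyte is male with probability p, independently.

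Under these assumptions males M and females F are independent Poisson with means λp and λ(1−p). Then:

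- Share of positive slides with no female = (e^(−λ(1−p)) − e^(−λ)) / (1 − e^(−λ)).
- Mean ratio over slides with at least one female = λp × E[1/F given F ≥ 1].
- True ratio = p / (1−p).

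Worked case, p = 0.3 and λ = 1:

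- No female: (e^(−0.7) − e^(−1)) / (1 − e^(−1)) = (0.4966 − 0.3679) / 0.6321 = 0.204.
- Mean ratio: E[1/F given F ≥ 1] = 0.833 when F has mean 0.7, so 1 × 0.3 × 0.833 = 0.25.
- True ratio: 0.3 / 0.7 = 0.43.

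The same formulas at other means:

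| Poisson mean λ | No female, 70% female | Mean ratio (true 0.43) | No female, 80% female | Mean ratio (true 0.25) |
|---|---|---|---|---|
| 1 | 20% | 0.25 | 13% | 0.16 |
| 2 | 13% | 0.41 | 8% | 0.26 |
| 5 | 2% | 0.56 | 1% | 0.33 |
| 10 | 0.09% | 0.52 | 0.03% | 0.29 |
| 20 | about 0 | 0.46 | about 0 | 0.27 |
| 50 | about 0 | 0.44 | about 0 | 0.26 |
| 100 | about 0 | 0.43 | about 0 | 0.25 |

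λ is the mean before restriction to positive slides; positive slides then average λ / (1 − e^(−λ)), which is 1.6, 2.3 and 5.0 for λ of 1, 2 and 5.

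The path is not monotone: too low at very small counts, close to the truth near 2, too high from about 3 to 20, then converging.

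Two arms with the same sex ratio (p = 0.25, true ratio 0.333) were simulated 4000 times with 15, 30 or 100 positive slides per arm. The average false difference in mean ratio, higher-count arm minus lower-count arm, was about +0.23 for λ of 1 against 5, +0.06 for 2 against 10 and −0.04 for 3 against 20. About 30% to 91% of cells held at least one undefined ratio. The pooled proportion male differed between arms by less than 0.003 on average in all nine scenarios.

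Two further checks, at p = 0.25 and λ from 0.5 to 100:

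- Overdispersed counts (negative binomial, size 1) give a weaker version of the pattern: the mean ratio ranges over 0.17–0.38, against 0.11–0.44 under Poisson counts.
- Adding 0.5 to both counts does not cure it: under Poisson counts the mean then runs from 0.95 at λ = 0.5 down to 0.34 at λ = 100.

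**The case against.** The best defence has four parts.

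- **The formula is inferred.** The SAP does not write it out, a pooled ratio is not expressly excluded, and the Month 32 and 50 text does not say mean. Slide reading follows a laboratory procedure and the table shells are held elsewhere; either might contain a rule for slides with no female. This stands as uncertainty, but it is a reason to state the formula in the SAP.
- **The problem fades.** Undefined slides are nearly gone by a mean of 10, and the bias is about 3% by 50. The documents give no gametocyte density, so the problem may be small here. This stands.
- **Little rests on the table.** SAP section 8 says "All other secondary endpoints should be interpreted descriptively", and the ratio is not even a listed secondary endpoint. This stands.
- **The pooled figure answers a slightly different question.** It weights by gametocyte, so a few dense slides can dominate, and it would itself shift with density if sex ratio varied with density. This is fair, but it does not rescue a per-slide ratio with zero denominators.

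A reader might also infer that the group mean cannot be formed at all. The documents do not support that: under the rule for missing laboratory results, the likely outcome is a mean over the slides that have a ratio, which is a selection problem.

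**Conclusion.** The point holds as a low-priority correction. On the plain reading, the planned summary most likely drops male-only slides, and at low counts its value depends on the count. Arms with an identical sex ratio could then show different values in either direction. At 70% female, for example, going from a mean of 1 to a mean of 5 moves the expected value by 0.56 − 0.25 = 0.31, against a true ratio of 0.43 in both arms.

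These sizes rest on assumed Poisson counts and an assumed sex ratio. The documents supply neither, nor the expected number of positive slides, so the size in this trial is unknown and could be negligible if counts are high.

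Two stronger readings are tempting. One is that any vaccine effect on gametocyte count would change the printed ratio. The non-monotone path rules that out: different counts can print the same value. The other is that a conclusion about transmission is at risk. SAP 7.3.1.1 links transmission potential to the prevalence of blood-stage infection and does not mention sex ratio. No efficacy conclusion depends on this table.

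**What to change.** In SAP 7.3.1.3 and 7.3.2.1, replace the mean male/female ratio with the proportion male: total males divided by total sexed gametocytes, per group, visit and site. Beside it print the number of positive slides, the number of gametocytes counted and the number of slides with no female. If a ratio is wanted, give total males over total females. A 95% confidence interval clustered on child is optional.

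The cost is a line of text in each section and a few extra columns. No data are needed beyond the male and female counts that the planned ratio already requires. The small downside is the extra weight given to dense slides, which the accompanying counts make visible.
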